7.4 Reporting Procedures

Study progress and safety will be reviewed bi-weekly by the Principal Investigator. Progress reports, including participant recruitment, retention/attrition, and AEs will be provided to an

Independent Monitoring Committee for bi-annual reviews. An annual report will be compiled and will include a list and summary of AEs. In addition, the annual report will address (1) whether adverse event rates are consistent with pre-study assumptions; (2) reason for dropouts from the study; (3) whether all participants met entry criteria; (4) whether continuation of the study is justified on the basis that additional data are needed to accomplish the stated aims of the study; and (5) conditions whereby the study might be terminated prematurely. The annual report will be signed by the chair of the Independent Monitoring Committee and may be forwarded to the IRB, NCCIH, FDA, and industry collaborator, who will only provide study product. The IRB and other applicable recipients will review the progress of this study on an annual basis.

As noted above, all SAEs that are unanticipated or that may possibly be related to study participation are reported to the NIH within 48 hours of learning of the event, to the IRB and Independent Safety Board (oversight committee) within five business days of learning of the event. If an event, incident, experience, or outcome is life-threatening or fatal, the IRB must be notified by phone within 24 hours.

Any unexpected fatal or life-threatening suspected adverse reactions will be reported to the FDA no later than 7 calendar days after the initial receipt of the information.

Relevant data and safety information obtained for each study participant will be verified against the original source documents by the primary study coordinator after each visit, plus the data will be spot checked by the program manager or compliance office. As noted above, any identified discrepancies will be discussed with the Principal Investigator and reviewed at weekly meetings. The frequency of data review for this study differs according to the type of data, and is summarized in **Table 3**.

Table 3. Frequency of Data Review

Data type	Frequency of review	Reviewer
Participant accrual (adherence to protocol	Weekly	Principal Investigator
regarding demographics, inclusion/exclusion)		
Compliance to treatment	Bi-Weekly	Principal Investigator
Adverse event rates (injuries)	Bi-Weekly	Principal Investigator
 Participant Accrual Out of range (non-clinically significant) laboratory data; Compliance to treatment Adverse events and adverse event rates. 	Bi-Annually	Study Monitoring Board

This study will be stopped prior to its completion if: (1) the intervention is associated with adverse effects that significantly impact the risk-benefit ratio, (2) study recruitment or retention becomes futile, (3) any new information becomes available during the trial that necessitates stopping the trial; or (4) if oversight committee indicates stopping trial is necessary due to adverse event frequency or severity.

7.5 Follow-up for Adverse Events

All reported adverse events will be followed until they are *resolved or considered stable*. The study coordinator will document the severity of any reported adverse event based on a conversation with the participant or their emergency contact. Whenever possible, medical records will be obtained to provide additional information regarding the nature of any reported adverse event.

7.6 Safety Monitoring

A Data and Safety Monitoring Plan (DSMP) will be implemented, with the following procedures to ensure data and participants' safety:

- Study progress and safety (e.g. cumulative table of adverse events and serious adverse events) will be reviewed monthly (and more frequently if needed) by the principal investigator.
- Progress reports, including participant recruitment, retention/attrition, and adverse events will be provided to an Independent Monitoring Committee for bi-annual reviews. The Data and Safety Monitoring Committee for this study will consist of an established board, which has reviewed all studies conducted within the University of Florida's Pepper OAIC during bi-annual conference calls for the past seven years. This board consists of the following individuals: (1) [name]., Chair, an epidemiologist who has been involved in research for many years, (2) [name]., a biostatistician who has been involved with a number of clinical trials, and (3) [name]., a physician who has been involved in the conduct of clinical research for many years.
- We will also compile an annual report, which will include a list and summary of adverse events. In addition, the annual report will address:
 - 1) Whether adverse event rates are consistent with pre-study assumptions;
 - 2) Reasons for dropouts from the study;
 - 3) Whether all participants met entry criteria:
 - 4) Whether continuation of the study is justified on the bases that additional data are needed to accomplish the stated aims of the study; and
 - 5) Conditions whereby the study might be terminated prematurely.

The annual report will be signed by the chair of the Independent Monitoring Committee and will be forwarded to the IRB. The IRB and other applicable recipients will review the progress of this study on an annual basis.

The Data and Safety Monitoring Plan will also require that [name] report all significant serious adverse events (SAEs) that may be possibly related to the study participation to the NIH within 48 hours of learning of the event, and to the IRB and Independent Safety Monitoring Board within five business days of learning of the event. In addition, any unanticipated SAEs that may increase risk to participants or potential participants will be reported to the NIH within 48 hours and to the IRB within five business days of [name] learning of the event.

8. INTERVENTION DISCONTINUATION

Participants may be removed from the study for the following reasons: (1) Unacceptable toxicity (≥ grade 2 toxicity) related to administration of resveratrol using the NCI toxicity criteria; (2) participant voluntarily decides to withdraw; (3) participant non-compliance with the study protocol; or (4) intercurrent disease, medication use, or condition that would affect the assessment of the participant's status. With their permission, participants will continue to be followed if study intervention is discontinued. This study will be stopped prior to its completion if: (1) the intervention is associated with adverse effects that significantly impact the risk-benefit ratio, (2) study recruitment or retention becomes futile, (3) any new information becomes available during the trial that necessitates stopping the trial; or (4) if the oversight committee indicates that discontinuation of the trial is necessary due to adverse event frequency or severity.

9. STATISTICAL CONSIDERATIONS

9.1 General Design Issues

A parallel three arm design of placebo (A) vs. standard dose resveratrol (B) vs. high dose resveratrol (C) will be used to test the primary hypothesis that the unweighted average of the target population means B and C is the same as that of A. This will be tested at p=0.05 (two-sided) by a Satterthwaite-corrected contrast. The analysis does not require equal variances in the three target populations, nor does it require that the means for B and C are the same. As our dependent variable, we will use the difference between the post-test value (90 days) and baseline. The primary and secondary aims and hypotheses are listed below.

Specific Aim 1. To examine the effects of resveratrol treatment on mitochondrial function (State 3 and 4 respiration on permeabilized muscle fibers, COX, CS enzyme activities and mitochondrial DNA content) in muscle samples of older adults.

Hypotheses. Compared to placebo, resveratrol supplementation will increase mitochondrial respiration (State 3=primary outcome, State 4), COX, CS enzyme activities, and mitochondrial DNA content in muscle specimens from the *vastus lateralis*.

Specific Aim 2. To evaluate the effects of resveratrol supplementation on levels of PGC-1 α , AMPK, and sirtuins (SIRT1 and SIRT3) in muscle samples of older adults.

Hypotheses. Compared to placebo, resveratrol treatment will increase PGC-1α (primary outcome), AMPK, SIRT1, and SIRT3 levels in muscle specimens obtained from the *vastus lateralis*.

Exploratory Aims. Explore the effects of resveratrol supplementation on measures of physical function, metabolic risk factors, and changes in physical activity in older adults.

Hypotheses. Compared to placebo, resveratrol supplementation will (1) increase walking speed, (2) improve physical performance, (3) increase resistance to muscle fatigue, (4) reduce established metabolic risk factors (i.e. diastolic blood pressure and blood levels of insulin and glucose), and (5) increase levels of spontaneous physical activity.

The proposed study will be the first to test whether resveratrol improves muscle mitochondrial function, and the mechanisms that underlie this potential improvement in older adults. An important exploratory goal is to determine whether the hypothesized biological changes in the mitochondria

translate to improved physical function and reduction in metabolic risk profile. The long-term goal of this line of research is to examine biological mechanisms of resveratrol in human muscle, and to understand how these adaptations improve human health. The investigative team has expertise in all aspects of this multi-disciplinary research and a history of collaboration, making this team uniquely qualified to conduct this study.

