9.2 Sample Size and Analysis Methodology

A total of 60 participants will be randomized into one of three conditions: (1) 1000 mg/day resveratrol (n = 20), (2) 1500 mg/day resveratrol (n = 20), or (3) vegetable cellulose (n = 20). Conservatively, presuming a repeated measures correlation for a participant is 0.7 (baseline explains about 50% of the variation at the post test), a study of 18 completers in each of the three groups has 80% power to detect a difference of 0.69 standard deviations in this contrast. Secondarily, we shall contrast each pair of treatments using a two-sided t-test (Satterthwaite-corrected for potentially unequal standard deviations) with 80% power, to detect a difference of 0.81 standard deviations. All comparisons will be accompanied by point and 95% confidence intervals for effect sizes.

From a parallel study, we estimate that baseline STATE 3 mitochondrial respiration (Primary Outcome) will have a mean of about 120 and a standard deviation of about 40. Hence 0.69σ (0.81 σ) represents sensitivity to better than a 25% (30%) change from baseline for STATE 3 mitochondrial respiration, respectively.

Robustness of Methods absent missing data: Based upon our experience, STATE 3 is not expected to be outlier prone, making the t-test highly robust against non-normality, even for moderate size samples such as in this trial. In clinical studies, where the comparison is between a placebo and an active treatment, comparing changes between treatments from baseline to a post-test, it is expected that the variability in the control group (pure replication) will be smaller than that in the experimental group (replication plus treatment). The Satterthwaite method deals with this contingency, whether or not it really occurs in our trial. Of course, the most important aspects of the analysis are the point estimates and 95% confidence intervals for the mean differences between the three pairs of treatments. The Satterthwaite method will be used for these as well.

Missing Data: Since the analysis is primarily based on the second biopsy, missing data represent a potential problem.

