Sensitivity analysis for Baseline Imbalance: Using baseline BMI, Baseline STATE 3, and gender, but not treatment, we shall develop a prediction equation via a linear model for the final STATE 3 value. Next, we shall use the predicted value for those missing the final STATE 3 value, and conduct permutation t-tests for each pair of treatments, replacing missing values by the predicted value. The type of bias that this corrects for is that missing values by be disproportionate in the arms according to the baseline value. For example, high baseline BMI may have more missingness on one arm while low BMI has more missingness on another. While this analysis corrects for interaction between treatment and missingness for baseline covariates, it does not account for missingness that develops during the study based on treatment vs. control issues. For example, if the treatment is associated with some subjects getting a headache and this leads to withdrawal from the study, this sensitivity analysis will not cover that contingency.

Sensitivity analysis for withdrawals for patient related study events, recognizing the events may not be measurable. First, we shall try to get a follow-up biopsy on every subject, ideally at the end of month 3, whether or not the subject completes the study medication program. Second, we shall ask the subject to provide reasons for withdrawal, based on a brief questionnaire. Third, we shall compare the withdrawal rates for the three treatment groups via an exact chi-square analysis. While an approximately equal withdrawal rate is not necessarily indicative of resolution, it is a reasonable assessment to make. Finally, using repeated measures mixed models methods, we shall compare the BMI trajectories for withdrawals vs. non withdrawals, stratified for treatment as a surrogate to the question as to whether the event of withdrawal is related to how the subject is doing on the trial. The month one and month two data will be used, as that will be missing for month 3.

Secondary analyses derived from the biopsy will be analyzed as above, but the study is powered strictly around STATE 3. Analysis on secondary variables that have repeated measures will utilize linear mixed model analysis of variance with unstructured covariance for repeated measures. Sensitivity analyses will be done via t-tests, utilizing the Satterthwaite correction for changes from baseline to three months, with last observation carried forward for missing data.

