9.5 Outcomes

9.5.1 Primary Outcome

From a previous study, we estimate that baseline STATE 3 (Primary Outcome) will have a mean of about 120, and a standard deviation of about 40. Hence 0.69 σ (0.81 σ) represents sensitivity to better than a 25% (30%) change from baseline for STATE 3, respectively. Data on this outcome measure will be collected through a muscle biopsy procedure at the second baseline visit and at the second follow-up visit. Muscle biopsies will be performed by [name]. who has performed numerous muscle biopsies for several previous studies. Skeletal muscle samples will be obtained under local anesthesia from the *vastus lateralis* muscle using a percutaneous needle biopsy technique as previously described by our group.[62] The skin will be closed with steri-strips. Participants will be contacted by phone three days following this procedure, and will return for a wound check one week after the procedure date. Approximately 150-250 mg of muscle tissue is removed. Portions of the muscle will be immediately processed for permeabilized fiber high-resolution respiration measurements and a very small piece of tissue will be mounted in embedding medium and frozen in isopentane for future histochemical analysis. The remaining tissue will be immediately frozen in liquid nitrogen and stored at -80°C until analysis.

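### The primary State 3 analysis is an unadjusted change score, where baseline adjustment would cut the contrast variance by about 13%; separately, the stated 0.69 and 0.81 SD do not follow from the stated inputs

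*Combined protocol and SAP*

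**What the plan says.** Section 9.1 tests whether "the unweighted average of the target population means B and C is the same as that of A", two-sided at 0.05, with a Satterthwaite-corrected contrast. The outcome is the raw change: "As our dependent variable, we will use the difference between the post-test value (90 days) and baseline". No covariate is named.

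Section 9.2 rests the sample size on "presuming a repeated measures correlation for a participant is 0.7 (baseline explains about 50% of the variation at the post test") and states that "18 completers in each of the three groups has 80% power to detect a difference of 0.69 standard deviations in this contrast". For the pairwise t-tests it claims 80% power "to detect a difference of 0.81 standard deviations". The unit is the baseline SD of State 3, about 40 on a mean of about 120. Section 9.5.1 adds that these differences "represents sensitivity to better than a 25% (30%) change from baseline for STATE 3, respectively".

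On variances, section 9.2 says "it is expected that the variability in the control group (pure replication) will be smaller than that in the experimental group", but gives no ratio. Its only model containing baseline State 3 is in a sensitivity analysis: "Using baseline BMI, Baseline STATE 3, and gender, but not treatment, we shall develop a prediction equation via a linear model". That equation fills in missing final values and does not adjust the treatment contrast. The same section says that the study is powered on State 3 alone.

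**The concern.** The plan justifies its correlation by the share of post-test variation that baseline explains. That share is what a baseline-adjusted model removes, leaving 1 − 0.7² = 0.51 of the variance. The planned change score leaves 2(1 − 0.7) = 0.60. The primary analysis therefore gives up precision that the plan's own input says is available, in about 54 completers who each have two biopsies.

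Section 6.2.2 describes permuted blocks and mentions no stratification on baseline State 3, so chance imbalance is possible. With 18 per arm the baseline contrast has a standard error of √(1.5/18) = 0.289 SD, or about 11.5 State 3 units. The change score corrects for imbalance with a slope of 1 where the plan implies 0.7, so an imbalance of one standard error moves the estimate by 0.3 × 11.5, about 3.5 units.

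The second issue is reproducibility. If 0.69 and 0.81 do not come from the listed inputs, a reader cannot tell whether they are cautious or optimistic, because an input is missing or wrong.

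**Working it through.** **Inputs.** Contrast weights −1, ½, ½ (sum of squares 1.5), two-sided 0.05, Satterthwaite: section 9.1. Correlation 0.7, 18 completers per arm, 80% power, mean 120, SD 40: section 9.2. No variance ratio is given, so equal variances are taken first.

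**1. The plan's own figures.**
- Variance of the change: 2(1 − 0.7) = 0.60, in units of the squared baseline SD.
- SE of the contrast: √(0.60 × 1.5/18) = 0.2236. SE of a pair: √(0.60 × 2/18) = 0.2582.
- Satterthwaite df, contrast: 17 × 1.5²/(1 + 2/16) = 34. A pair also has 34.
- Noncentral t, 80% power: **0.645 SD (contrast) and 0.745 SD (pair)**, against the stated 0.69 and 0.81.
- Power at 0.69 and 0.81: 85.0% and 86.2% (84.9% and 86.1% in 200,000 simulated trials).

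**2. Could another reading give both figures?** With equal variances:

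| Departure from the stated inputs | Contrast | Pair |
|---|---|---|
| Normal approximation | 0.626 | 0.723 |
| df pooled over three arms | 0.639 | 0.737 |
| 16 completers per arm | 0.687 | 0.793 |
| 85% power | 0.690 | 0.796 |
| Correlation 0.65 | 0.697 | 0.804 |
| Residual variance 0.51 | 0.595 | 0.687 |

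None gives both. The correlation needed for 0.69 is about 0.657, and for 0.81 about 0.645.

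**3. Larger variance in the active arms (assumed multiples).** Change-score detectable differences when the active-arm 90-day SD is a multiple of the baseline SD:

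| Multiple, and what is held | Contrast | Active vs placebo | Active vs active |
|---|---|---|---|
| 1.1, correlation 0.7 | 0.656 | 0.766 | 0.787 |
| 1.2, correlation 0.7 | 0.671 | 0.793 | 0.838 |
| 1.3, correlation 0.7 | 0.688 | 0.825 | 0.897 |
| 1.1, covariance 0.7 | 0.679 | 0.808 | 0.865 |

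No ratio gives 0.69 for the contrast and 0.81 for every pair. At 1.2 with the correlation held, power at the stated differences is 82% (contrast), 82% (active vs placebo) and 77% (active vs active).

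**4. Gain from baseline adjustment.**
- Large-sample variance ratio: 0.51/0.60 = 0.85.
- Allowing for an estimated common slope (51 within-arm df): 0.85 × (1 + 1/49) = 0.867, a **13% reduction**. Simulations of 200,000 trials gave 13.0% and 13.3%.
- Equivalent completers per arm: 18/0.867 = 20.8.
- Other correlations, equal SDs, 1 − [(1 + r)/2] × 50/49: 23% (r = 0.5), 18% (0.6), 8% (0.8).
- Active-arm SD 1.1, 1.2 and 1.3 times, correlation 0.7: 10%, 7% and 5%. At correlation 0.8 and 1.3 times the gain is nil.
- Adjusted detectable differences, equal variances: 0.5945 × √(50/49) = 0.601 and 0.6865 × √(50/49) = 0.693. Simulated power was 79.8% at 0.60 and 79.5% at 0.69, with type I error 5.0% and 4.8%.
- Adjusted power at the stated 0.69 and 0.81: about 90% and 91%.

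**5. In State 3 units.** Contrast as stated: 0.69 × 40 = 27.6 (23% of 120). Change score: 0.645 × 40 = 25.8 (21.5%). Adjusted: 0.60 × 40 = 24 (20%). The pair goes from 0.81 × 40 = 32.4 (27%) as stated to 0.745 × 40 = 29.8 (24.8%). The 25% and 30% statements remain true.

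**The case against.** The change score is pre-specified, unbiased and defended in section 9.2. On the plan's inputs with equal variances it exceeds its 80% target, so no conclusion becomes invalid if it stays. This is correct, and it is why the point concerns efficiency.

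A stronger objection is that the 13% assumes equal variances, which the plan does not expect. If treatment adds variance while the covariance stays at 0.7, an active-arm SD of 1.1 times baseline gives 0.679 and 0.808 for the contrast and active vs placebo, close to the stated pair. At 1.2 times it gives 0.715 and 0.872, and the stated figures are no longer conservative. On this view 0.69 and 0.81 may simply carry an undisclosed variance allowance.

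Part of this stands. The mismatch is conservative only under equal or mildly unequal variances, and any unequal-variance figure must say what is held constant. But the gain persists under held covariance (8–10% at 1.2 to 1.3 times). The active-vs-active comparison, which the 0.81 also covers, would then need 0.865 at 1.1 times. An allowance that is not written down cannot be credited.

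Arm-specific slopes would cost more than one degree of freedom; the equal-variance gain would be about 11%. The common-slope model proposed below keeps type I error at about 5% under unequal variances as well.

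**Conclusion.** Both parts hold. The unadjusted change score is valid but less precise than a baseline-adjusted analysis: about 13% more variance could be removed at a correlation of 0.7 with 18 completers per arm, equal SDs and a common slope. With larger active-arm SDs (1.1 to 1.3 times) and the correlation held, the gain is 10% to 5%; it vanishes only in the most extreme case examined, correlation 0.8 with 1.3 times.

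The detectable differences of 0.69 and 0.81 SD are not reproducible from the stated inputs. With equal variances they overstate what is needed, so the sample size is not undermined. The missing item is the variance assumption, or a lower correlation. The revision should be made, but it does not call the trial's validity into question.

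**What to change.** - **Primary model (section 9.1):** 90-day State 3 on arm and baseline State 3 with a common slope, arm-specific residual variances, Satterthwaite degrees of freedom and the same contrast, (B + C)/2 − A, two-sided at 0.05. Keep the raw change as a sensitivity analysis.
- **Detectable differences (sections 9.2 and 9.5.1):** about 0.60 SD (contrast) and 0.69 SD (pair), labelled as assuming equal variances. Add a line for larger active-arm variance that states its assumption. For example, at 1.2 times with the correlation held at 0.7 the adjusted model detects about 0.645 (contrast) and 0.77 (active vs placebo); with the covariance held instead, about 0.677 and 0.832.
- **If the change score stays primary:** state 0.645 and 0.745 SD, or state the extra assumption that leads to 0.69 and 0.81.
- The 25% and 30% wording can stay.

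The cost is protocol and SAP text and one residual degree of freedom; baseline State 3 already comes from the baseline biopsy. Because section 6.2.3 says that the statistician is not blinded, the model should be fixed before outcome data are seen by arm.
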